8.5 Handling of Missing Data

Complete case analysis will be conducted as long as the fraction of missing values for “composite adverse events until day 30” and “antibiotic exposure” (“short antibiotic treatments” and “antibiotic exposure at discharge”) remain in the range of up to 5%. If the number of missing values turns out to be above 5%, an additional analysis will be conducted using **multiple or Bayesian imputation**. In any case, the possible impact of missing values on study results will be assessed by **sensitivity analysis** using worst-case and best-case imputations.

8.6 Statistical Analysis

8.6.1 Descriptive Statistics

The first step of statistical data analysis will comprise the application of conventional data cleaning and checking procedures including assessment of missing data and outliers, and uni- and bivariate plausibility checks. Data verifications and if applicable corrections will be requested.

Next, a thorough description of the overall study sample and of the two randomized study arms will be conducted for the two analysis populations ITT and PP. Frequency counts will be used for nominal variables and means with standard deviations or medians with inter-quartile ranges will be used for numerical variables as appropriate. Statistical hypothesis tests will be used to check the success of

randomization, e.g. chi-square test, Wilcoxon signed-rank test or t-test.

8.6.2 Primary Analysis of Antibiotic Exposure

The primary endpoint “short antibiotic treatments” will be analyzed for superiority. We will assess the differences in proportions by Bayesian analysis assuming binomially distributed events (beta-distributed study-arm specific probabilities) and uninformative uniform priors.

More specifically, the following generative model will be used:

$$N_{PCT}^s \sim \text{Binomial}(N_{PCT}, p_{PCT})$$

$$N_{ctrl}^s \sim \text{Binomial}(N_{ctrl}, p_{ctrl})$$

$$p_{PCT}, p_{ctrl} \sim \text{Uniform}(0, 1)$$

with

N_{PCT}^s, N_{ctrl}^s : number of patients with shortABx of the PCT arm and control arm, respectively

N_{PCT}, N_{ctrl} : number of patients randomized to the PCT arm and control arm, respectively

p_{PCT}, p_{ctrl} : shortABx probability for patients of the PCT arm and control arm, respectively

Differences between study-arm specific probabilities will be computed by Monte Carlo simulation with sampling from study-arm specific posterior probabilities. Success of the analysis of antibiotic exposure is specified by more than 98.5% ¹ posterior probability for more frequent short antibiotic treatments in the PCT arm than in the control arm, i.e.,

$$\text{Probability}[\text{prob(short-ABx | PCT arm)} > \text{prob(short-ABx | control arm)}] > 98.5\%$$

with

$\text{prob(short-ABx | PCT arm)}$: probability of short antibiotic treatment
for patients randomized to the PCT arm,

$\text{prob(short-ABx | control arm)}$: probability of short antibiotic treatment
for patients randomized to the control arm.

The primary analysis will be conducted based on the ITT population. The analysis will also be conducted based on the PP patient populations and ITT- and PP-results will be compared and discussed.

8.6.3 Secondary Analysis of CAE30

The first secondary endpoint “composite adverse events until day 30” (CAE30) will be analyzed for safety non-inferiority of the PCT arm vs. the control arm on the basis of the PP patient population. The analysis will also be conducted on the basis of the ITT patient populations and ITT- and PP-results will be compared and discussed. Differences in proportions of CAE30 between PCT arm and control arm will be assessed by Bayesian analysis assuming binomially distributed events (beta-distributed study-arm specific CAE30 probabilities) and uninformative uniform priors. More specifically, the following generative model will be used:

$$NE_{PCT} \sim \text{Binomial}(N_{PCT}, p_{PCT})$$

$$NE_{ctrl} \sim \text{Binomial}(N_{ctrl}, p_{ctrl})$$

$p_{PCT}, p_{ctrl} \sim \text{Uniform}(0, 1)$

with

NE_{PCT}, NE_{ctrl} : number of patients with CAE30 of the PCT arm and control arm, respectively

N_{PCT}, N_{ctrl} : number of patients randomized to the PCT arm and control arm, respectively

p_{PCT}, p_{ctrl} : CAE30 probability for patients of the PCT arm and control arm, respectively

Differences between study-arm specific CAE30 probabilities will be computed by Monte Carlo simulation sampling CAE30 probabilities p_{PCT}, p_{ctrl} from their analytically computed study-arm specific posterior probabilities. Study success is specified by more than 98.5%¹ posterior probability for a CAE30 probability of patients of the PCT arm smaller than the CAE30 probability of patients of the control arm plus 10% (NI margin):

Probability(CAE30 probability of PCT arm < CAE30 probability of control arm + 10%) > 98.5% ¹,

or with the above introduced notation

Probability($p_{PCT} < p_{ctrl} + 0.1$) > 98.5% ¹.

8.6.4 Secondary Analysis of Antibiotic Exposure

The second secondary endpoint “antibiotic exposure at discharge” will be analyzed for superiority. We will assess the differences in proportions by Bayesian analysis assuming binomially distributed events (beta-distributed study-arm specific probabilities) and uninformative uniform priors. More specifically, the same generative model will be used as the one for short antibiotic treatments (see Section 8.6.2). Differences between study-arm specific probabilities will be computed by Monte Carlo simulation with sampling from study-arm specific posterior probabilities. Success of the analysis of antibiotic exposure at discharge is specified by more than 98.5%¹ posterior probability for less antibiotic exposure of the PCT arm than of the control arm, i.e.

Probability[prob(discharge-ABx | PCT arm) < prob(discharge-ABx | control arm)] > 98.5%

with

prob(discharge-ABx | PCT arm) : probability of prescribed antibiotics at hospital discharge for patients randomized to the PCT arm

prob(discharge-ABx | control arm) : probability of prescribed antibiotics at hospital discharge for patients randomized to the control arm

The analysis will be conducted first based on the ITT population. The analysis will also be conducted based on the PP patient populations and ITT- and PP-results will be compared and discussed.

8.6.5 Further Secondary and Exploratory Analysis

¹ Simulation of the selected adaptive Bayesian design with specified interim analyses based on 200, 350, 550, and 650 patients showed that the one-sided type-I error was controlled to be below 2.5% by choosing the value 98.5% as the threshold for study success. See [SAP4.0] for more information.

Secondary and exploratory endpoints will be analyzed according to variable type:

Numerical endpoints:

Distributions of numerical variables will be visualized for all patients and separately for PCT and control arm. Study arm-specific distributions will be compared with each other by statistical tests (e.g. Wilcoxon rank-sum tests), and by comparing descriptive summary measures (e.g. group medians and means).

Binary endpoints:

2 x 2 contingency tables will be reported for counts stratified according to study arm (PCT, control) and endpoint level (true/false). Associations between study arms and endpoints will be analyzed by statistical tests (e.g. chi-square test or Fisher's exact test). Proportions and two-sided 95% confidence intervals or Bayesian credible intervals will be computed for all patients and separately for PCT and control arm.

8.7 Sensitivity Analysis

Sensitivity analysis will be conducted to assess the robustness of primary and secondary analysis results.

- The results obtained for ITT and PP patient population will be compared and discussed.
- Safety analysis (as described in Section 4.4) will also be conducted for the alternative safety endpoint definition CAE30' only counting safety adverse events that occur at least 24 hours after patient randomization. The results will be compared and discussed with the results for counting all safety adverse events after patient randomization.
- For endpoints CAE30, shortABx, and prescribedABx the study-arm specific proportions will be compared and discussed with the corresponding proportions that were obtained for the two run-in studies that were performed for accurate calculation of sample size and required power; these first two ProSAVE pilot-level study batches were named "ProSAVE-1 & -2" (comprising 95 (ITT) and 60 (PP) non-COVID patients not transferred to ICU within 24 hours, patients enrolled from 2020-05-28 to 2021-02-24).
- The safety endpoint CAE30 will be analyzed and discussed regarding its individual constituent adverse event variables.

8.8 Sample Size

We plan to enroll an adequate number of patients for the study by a Bayesian adaptive design with a maximum number of 700 patients and interim analyses after the enrollment of 200 patients, 350 patients, 550 patients and 650 patients.

Sample size estimation was based on the observed results of the first two ProSAVE pilot-level study batches, see Table 8.1 (analysis population and endpoint specific results; "ProSAVE-1 & -2" comprising 95 (ITT) and 60 (PP) non-COVID patients not transferred to ICU within 24 hours, patients enrolled from 2020-05-28 to 2021-02-24). 5000 clinical trials were simulated per analysis setting (study endpoint, analysis population and assumed fixed sample size from 200 to 700 patients) with the distribution of events according to predictive posterior distributions (computed for the assumed sample sizes from pilot posterior probability distributions derived with uninformative conjugate priors). The corresponding statistical power estimates were determined as the proportions of study successes when applying the analyses and success criteria specified in Section 8.6.

We considered a sample size of about 500 patients to be adequate for the study because a statistical power of 90% was reached with 500 patients for the safety endpoint CAE30 assuming pilot ITT results.

In order to account for additional sources of variation and missing data, e.g. due to seasonal changes during the year, possible influences of a potential fourth wave of COVID-19 and the inclusion of additional study sites, we specified the study design in an adaptive way with planned interim analyses after 200, 350, 550 and 650 patients and a maximum number of 700 enrolled patients.

Table 8.1: Pilot study results for the safety endpoint “CAE30” and for the antibiotic exposure endpoints “shortABx” and “prescribedABx” for ITT and PP patient populations.

Simulation scenario			Pilot study results			
n	Endpoint	Data	PCT		Control	
			n	n _{pos}	n	n _{pos}
1	CAE30	pilot, ITT	48	3	47	10
2		pilot, PP	30	1	30	7
3	shortABx	pilot, ITT	48	14	47	5
4		pilot, PP	30	12	30	3
5	prescribedABx	pilot, ITT	47	15	46	24
6		pilot, PP	30	7	29	19

Table 8.2: Estimation of statistical power (i.e. proportion of simulated trials reaching study success) for the three study endpoints “CAE30”, “shortABx” and “prescribedABx” with fixed sample sizes from 200 to 700 patients (total; 100 to 350 patients per study arm) assuming effect sizes (estimate and uncertainty) of the “ProSAVE-1 & -2” pilot data results.

Data	# Patients		Statistical Power		
	Total	Per arm	CAE30	shortABx	prescribedABx
pilot, ITT	200	100	79%	82%	76%
	300	150	84%	86%	81%
	400	200	87%	90%	86%
	500	250	90%	92%	87%
	600	300	91%	93%	88%
	700	350	92%	94%	90%
pilot, PP	200	100	88%	94%	98%
	300	150	91%	96%	99%
	400	200	93%	97%	99%
	500	250	93%	98%	100%
	600	300	95%	98%	99%
	700	350	95%	98%	100%

The adequacy of the study design was re-assessed for the following changes: (a) exchange of primary endpoint and (first) secondary endpoint (new primary endpoint: shortABx, new first secondary endpoint: CAE30), (b) change of CAE30 inference from superiority to non-inferiority, and (c) change of

the times of interim analyses from 500 and 600 patients to 550 and 650 patients, respectively. The evaluation of the study design was done analogously to the initially applied method described in Section 2.3.2 of [SAP3.0] (clinical trial Monte Carlo simulations based on pilot study results). The new simulations (including some improved approximations of protocol and data generation) for the implemented changes resulted in an increase of the analysis parameter γ from 0.9785 to 0.985 in order to keep type-I error control at 2.5%. We valued the new design adequate with statistical powers of 99%, 75% and 48% to show shortABx superiority, CAE30 non-inferiority and prescribedABx superiority, respectively, assuming half of the effects observed in the pilot study concerning antibiotic exposure ($RR_{shortABx} = 1.9$ and $RR_{prescribedABx} = 0.8$) and considerably smaller CAE30 effects than observed in the pilot study ($RR_{CAE30} = 0.9$ for one tenth of the effect observed in the pilot study).

8.9 Interim Analyses

Interim analyses will be conducted after the enrollment of 200 patients, 350 patients, 550 patients and 650 patients.

After the enrollment of 200 and 350 patients an interim analysis will be conducted applying a criterion for potentially *stopping for futility*. A non-binding recommendation to stop patient enrollment for futility will be given if interim results are not in a “promising zone” to reach the CAE30 success criterion. More specifically, the stopping recommendation will be given if the posterior predictive probability of CAE30 success (i.e., proving non-inferiority) with the maximum number of 700 patients is below a specific futility cut-off $\Theta_{F_N} = 0.1$ with $N = 200$ or 350 representing the respective enrollment status:

Probability(CAE30 success with 700 patients | interim data) $< \Theta_{F_N}$, i.e.

Probability(Posterior predictive probability($p_{PCT} < p_{ctrl} + 0.1$, 700 patients | interim data) $> 98.5\%^1$) < 0.1

After the enrollment of 550 and 650 patients an interim analysis will be conducted applying criteria to stop potentially (a) for futility or (b) for study success:

a. *Stopping for futility:*

A non-binding recommendation to stop patient enrollment for futility will be given if interim results are not in a “promising zone” to reach the CAE30 success criterion. More specifically, enrollment will be stopped if the posterior predictive probability of CAE30 success with the maximum number of 700 enrolled patients is below a specific futility cut-off $\Theta_{F_N} = 0.1$ with $N = 550$ or 650 representing the respective enrollment status:

Probability(CAE30 success with 700 patients | interim data) $< \Theta_{F_N}$, i.e.

Probability(Posterior predictive probability($p_{PCT} < p_{ctrl} + 0.1$, 700 patients | interim data) $> 98.5\%^1$) < 0.1

b. *Stopping for success:*

Enrollment will be stopped for success if interim results reveal a sufficiently high probability that success criteria are reached for the endpoints CAE30, shortABx and prescribedABx. More specifically, enrollment will be stopped if the posterior predictive probabilities of the three endpoints CAE30, shortABx and prescribedABx for the respective number

of enrolled patients are above the cut-off $\Theta^s_N = 0.9$:

Probability(CAE30 success with enrolled patients | interim data) > Θ^s_N AND
Probability(shortABx success with enrolled patients | interim data) > Θ^s_N AND
Probability(prescribedABx success with enrolled patients | interim data) > Θ^s_N

Note: Use of the posterior predictive probability will allow to conduct the interim analysis in a timely manner without the need to wait for the completion of the 30 days follow-up times of all patients. Thereby, missing or incomplete endpoint data of enrolled patients will be imputed by predicted endpoint data including its respective level of uncertainty.

The cut-off parameters of the stopping criteria Θ^F_{200} , Θ^F_{350} , Θ^F_{550} , Θ^F_{650} , Θ^s_{550} and Θ^s_{650} were specified by numerical simulations as $\Theta^F_{200} = \Theta^F_{350} = \Theta^F_{550} = \Theta^F_{650} = 0.1$ and $\Theta^s_{550} = \Theta^s_{650} = 0.9$ to assure a sufficiently controlled one-sided type-I error < 2.5% and a sufficiently high statistical power (study success probability) assuming pilot study results, see [SAP3.0].

8.10 Safety Analyses for DMC (See DMC Charter for detailed information)

Safety analyses will be conducted at least twice when 350 and 550 patients are enrolled. The DMC will receive corresponding safety datasets and safety relevant interim analysis results:

- a. Safety datasets will be on patient level and comprise at least the following information: study arm assignment, CAE30, and all single binary CAE30 endpoint components. The DMC may request additional data at its discretion.
- b. As safety relevant interim analysis results the DMC will receive:
 - a. A contingency table of study arm (PCT, control) vs. safety endpoint CAE30 (event occurred yes/no/NA; NA for patients with incomplete follow-up and no event yet)
 - b. 95% credible intervals of study-arm specific CAE30 probabilities and of the difference in CAE30 probability between study arms (complete case analysis)
 - c. Posterior probability distributions on the basis of all patients with CAE30 data (complete case analysis) of
 - a. study-arm specific posterior probability distributions of CAE30
 - b. the difference in CAE30 probability between study arms
 - d. Predictive posterior distributions on the basis of all enrolled patients (including patients with missing or incomplete CAE30 data) of
 - a. study-arm specific posterior probability distributions of CAE30
 - b. difference in CAE30 probability between study arms

8.11 Health Economic Evaluation

The clinical outcomes of the study will be analyzed from a health economic hospital perspective, extrapolation to third party payer remains optional. Clinical data and local cost data will be processed in the previously published/under publication Health Economic Model (Janne C Mewes et. al., The cost impact of PCT-guided antibiotic stewardship versus usual care for hospitalized patients with suspected sepsis or lower respiratory tract infections in the US: a health economic model analysis).²⁸ All available information will be used in the model. Missing/confidential cost data will be substituted with publicly available data and highlighted accordingly.

These clinical parameters will be multiplied with the respective cost per unit, e.g. 1 day of mechanical ventilation, and its differences will be calculated, to understand the changes in cost when using PCT. All cost results per clinical parameter will be aggregated to average cost of 1 patient of each group, finally the cost of each study group will be modelled.

All findings will be discussed in the local hospital context as well as how these compare to the overall situation in the United States.

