Primary Objective	Determine the difference in antibiotic exposure and healthcare cost and assess safety by comparing antibiotic prescription guided by a (i) PCT algorithm + stewardship team (intervention) or (ii) standard guidelines (control) in hospitalized patients with suspected or confirmed LRTI.
Study Design	Prospective, multi-center, randomized-controlled interventional trial
Enrolling Wards	ED, admitted floor and ICU teams
Intervention	Addition of previously validated PCT algorithms to clinical assessment to guide the discontinuation of antibiotics in patients with suspected or confirmed pneumonia.
Primary Endpoint	Proportion of patients with short treatment of pneumonia with antibiotics (less than 4 days, "shortABx")
Secondary Endpoints	
 1. Composite safety adverse event rate at 30 days (CAE30). The composite endpoint includes: 
 a. All-cause in-hospital mortality b. All-cause mortality after discharge (as available) c. Hospital readmission d. Septic shock (vasopressor use for > 1 h) e. Mechanical ventilation (via endotracheal tube for respiratory failure) f. Required dialysis g. Lung abscess/empyema 2. Antibiotic exposure at discharge 3. Antibiotic duration 4. Days of Therapy per 1000 patient days (inclusive of antibiotics prescribed at discharge) 5. Antibiotic days prescribed at discharge 6. Treatment or readmission for CDI until day 30 after enrollment 7. LOS in hospital until Day 30 8. LOS on ICU until Day 30 9. ICU admission until Day 30
Exploratory Endpoints	All the single variables of the safety endpoint CAE30, see 3.2. "Composite adverse events until day 30"
Healthcare Economic Endpoints	
Costs associated with primary hospitalization, readmission for CDI, and loss of function
 
 • Cost of Antibiotics (total cost of antibiotics per patient inclusive of antibiotic, tubing, IV bag, discharge antibiotic prescription) • Cost of Procalcitonin • Total per patient cost (including blood cultures and mechanical ventilation days)

	
 • Antibiotic ADRs (e.g. CDI) • AB days difference plus prescriptions avoided infection adverse event incidence modeling²⁹ • Cost of readmissions

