3 TRIAL OBJECTIVES

3.1 Primary Objective

Determine the difference in antibiotic exposure and healthcare cost and assess safety by comparing antibiotic prescription guided by a (i) PCT algorithm + stewardship team (intervention) or (ii) standard guidelines (control) in hospitalized patients with suspected or confirmed pneumonia.

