4 STUDY DESCRIPTION

4.1 Study Design

The study will be conducted as a prospective, randomized controlled, multicenter, interventional trial whereby individual patients will be evaluated for eligibility and then randomized to one of two arms:

- (i) Antibiotic prescription guided by a PCT algorithm and stewardship team (PCT arm): antibiotic treatment recommendations will be made by the stewardship team. The stewardship team will discuss PCT algorithm overruling with the primary care team.
- (ii) antibiotic prescription guided by current guidelines (control arm): treating clinicians will be blinded to PCT results and antibiotic treatment decisions will be at the discretion of the treating clinician based on standard of care guidelines.

Antibiotic exposure (duration and DOT), safety outcomes and associated healthcare costs will be compared between groups throughout enrollment and follow up.

Screening, (D0) Baseline and (D1) PCT measurement

Patients will be consecutively screened for eligibility one day after their admission to an inpatient bed. Research staff will be responsible for screening admissions and antibiotic orders for potential enrollment and randomization. A dedicated stewardship team at each site will implement the intervention algorithm. The stewardship team will ensure PCT results and appropriate algorithm interventions are addressed (via phone, email, messaging system, or in person) with the primary provider as well as document assigned protocol adherence and deviations.

Upon review of inclusion/exclusion criteria, study subjects will be randomized 1:1 into one of two groups: (i) PCT algorithm + stewardship team arm or (ii) the standard care arm. PCT results will be unblinded in the (i) PCT algorithm + stewardship team arm and blinded in the (ii) standard care group.

Potential subjects resulting from the initial EPIC screen are not considered subjects. Subjects are defined as those who meet criteria for entry into the study. Non-eligible subjects are those who have met an exclusion criterion at some point during the study.

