Upon randomization, the research staff will send a welcome message to both the standard of care and intervention teams. Enrollment PCT values consist of one value from the day of randomization (D1) and one value from a previous day 6-48 hours prior (D0). All PCT measurements throughout the study should be obtained using discarded blood from routine lab work. All PCT values ordered by the study team for patients in the intervention arm will be released in EPIC, while those of the standard of care arm will be suppressed.

After the PCT results are available, the stewardship team will review both the D0 and D1 results as a pair and provide an antibiotic recommendation (PCT intervention arm only) using the stewardship team recommendation template to the primary provider service on enrollment day. If the stewardship team is discordant with the PCT algorithm (see section 1.5 for algorithm), they will be sent a discordance survey (see Appendix G). If the primary team is discordant with the stewardship recommendations, a reason for discordance survey will be sent out and recorded in REDCap (see Appendix H). Patient information will be recorded in REDCap for both the intervention and standard of care arms.

(D2+) Daily PCT measurements

For patients who are still eligible and on antibiotics, PCT should be measured daily for one week and then Monday, Wednesday, and Friday in both arms. If there are no results on a Monday, the PCT will be measured on Tuesday, Wednesday, and Friday. If there are no results on a Wednesday, the PCT will be measured on Monday, Thursday, and Friday.

For PCT arm patients, the stewardship team will review available PCT results and provide an antibiotic recommendation to the primary provider service on the same calendar day. Antibiotic monitoring and/or discontinuation will be guided by clinical assessment (medical history, physical exam, imaging and standard laboratory evaluations) as well as the PCT algorithm (Appendix A, LRTI) and pre-defined overruling criteria (Appendix A, 11.2). If the stewardship team is discordant with the PCT algorithm, a discordance survey will be requested (Appendix G). In case of discordance between the primary team and the stewardship team, a discordance survey will also be requested (Appendix H).

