7.2 Healthcare Resource Utilization Data

- **Cost of Antibiotics** (total cost of antibiotics per patient inclusive of antibiotic, tubing, IV bag, discharge antibiotic prescription)
- **Total per patient cost** (including blood cultures and mechanical ventilation days)
- **Antibiotic ADRs (e.g. CDI)**
- **AB days difference plus prescriptions avoided, and infection adverse event incidence modeling²⁹**
- **Cost of readmissions**
- **Cost of Procalcitonin**

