8.1.2 Study goal

The study goal is to validate that a specified PCT algorithm applied to non-COVID-19 patients hospitalized with suspected pneumonia

1. reduces antibiotic exposure specified as an increase of *short* antibiotic pneumonia treatments lasting less than 4 days,
2. is not inferior concerning safety according to composite adverse events until day 30, and
3. reduces antibiotic exposure specified as a decrease of antibiotics prescribed at discharge for pneumonia treatment.

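### The cost comparison lists no item for the stewardship team's time, so unless the external model adds it, a cost specific to the PCT arm is left out and the comparison favours PCT

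*Protocol*

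**What the plan says.** Healthcare cost sits in the primary objective (Protocol synopsis and 3.1), beside antibiotic exposure and safety. The arms are the PCT algorithm plus stewardship team, and standard guidelines.

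Section 4.1 describes the team's work: "A dedicated stewardship team at each site will implement the intervention algorithm". The team reviews the first two PCT results as a pair and is to "provide an antibiotic recommendation (PCT intervention arm only) using the stewardship team recommendation template to the primary provider service on enrollment day". Further recommendations follow on weekdays with a PCT result, unless a standing recommendation has been declared. The team also documents adherence and deviations, and disagreements trigger discordance surveys. Control-arm PCT results are withheld from both the stewardship and the primary teams.

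The cost items, in the synopsis and again in 7.2, are antibiotics (with tubing, IV bags and discharge prescriptions), "Cost of Procalcitonin", a total per patient that mentions blood cultures and ventilation days, antibiotic adverse reactions, modelled events avoided, and readmissions. The synopsis introduces its list with "Costs associated with primary hospitalization, readmission for CDI, and loss of function".

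Section 8.11 takes a hospital perspective, passes clinical and local cost data to an external health economic model, and prices clinical quantities ("These clinical parameters will be multiplied with the respective cost per unit") "to understand the changes in cost when using PCT". The SAP has no health economic section.

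**The concern.** A cost comparison should charge each arm for what that arm consumes. Here the intervention has two components, a test and a team, and only the test has its own cost line. If the team's contacts shorten treatment, the antibiotic savings appear in the PCT arm's cost while the staff time that helped to produce them may not.

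Two things are at stake. The first is the size of the reported cost difference, which would look better for PCT than it should. The second is what the figure is taken to mean. Section 8.11 presents it as the change in cost from using PCT, and 8.1.2 speaks of the algorithm alone ("The study goal is to validate that a specified PCT algorithm applied to non-COVID-19 patients"). The synopsis and 3.1 define the contrast as algorithm plus team. A hospital that bought only the assay could misread the result as its own expected saving.

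**Working it through.** The documents state no cost, unit cost or cost difference, so there is no figure to reproduce. The check compares the components of the intervention with the cost items, then works out the direction and a possible size.

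**Components against cost items**

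| Component | Where described | Own cost item? | Quantity collected? |
|---|---|---|---|
| PCT assay | 4.1, 5.1, 6.2 | Yes (synopsis, 7.2), not assigned to an arm | Yes, PCT values (7.1) |
| Stewardship review and recommendation, PCT arm only | 4.1 | No | Contacts appear countable from documentation; no staff time in 7.1 |
| Discordance follow-up | 4.1, Appendices F and G | No | Surveys and overruling reasons; no staff time |

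The contacts should be countable because 4.1 has the team document adherence, and because PCT-arm membership of the per-protocol population (8.4) depends on recommendations having been given. What is missing is minutes per contact and a staff rate.

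**Direction**

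Let c be the team's cost per PCT-arm patient and f the share of it that is incremental to usual care (0 to 1). If c is left out,

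reported difference (PCT − control) = true difference − f × c.

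For any f above 0 the reported difference is too low, which favours PCT.

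**Size, on assumed inputs only**

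c = recommendations per patient × minutes / 60 × hourly staff cost

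- Low: 1 × 10/60 × 60 USD = 10 USD
- Middle: 3 × 20/60 × 100 USD = 100 USD
- High: 5 × 30/60 × 150 USD = 375 USD
- With a sixth contact: 6 × 30/60 × 150 USD = 450 USD

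These values are for f = 1. With f = 0.5 they halve to 5, 50, 187.50 and 225 USD. None of these inputs is in the documents.

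**Assay cost**

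PCT is measured in both arms (5.1), but control results are suppressed and serve the study only. With price a and mean numbers of tests n(PCT) and n(control), charging both arms contributes a × [n(PCT) − n(control)] to the difference. Charging the PCT arm alone contributes a × n(PCT). Testing stops when antibiotics stop (1.6), so if PCT-arm patients stop sooner, the first rule could make the assay look like a saving. The protocol does not say which rule applies.

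**Loss of function**

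The synopsis names it as a cost. No item in 7.1 or 7.2 captures it, 8.11 does not mention it, and the stated perspective is the hospital's.

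**The case against.** A reader might infer that the cost objective is biased as written and that the PCT arm is charged for the assay alone. The documents do not support that.

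- **The model is not shown.** The title of the external model in 8.11 refers to PCT-guided stewardship against usual care, so it may already carry a stewardship cost. Section 8.11 also says that all available information will be used, and the total per patient is open-ended. An item that is not specified is not the same as one that is excluded. This stands, and it makes the bias conditional. It does not close the gap: the protocol itemises tubing and IV bags, yet names no staff time and collects none.
- **The time may not be fully incremental.** The documents do not say whether sites already fund stewardship that also reaches control patients. This stands, and it is why f appears above. The PCT-based recommendations are confined to one arm by design, so some difference in workload is likely, but the full amount cannot be called bias.
- **The assay is not assigned to an arm.** This stands, and it is a second unstated rule.
- **The dollar range is assumed.** This stands. It shows scale and is not an estimate.
- **The contrast is already named correctly.** The synopsis, 3.1, 4.1 and 6.1 all name the team. This largely stands: the labels in 8.1.2 and SAP 1.2 are shorthand and do not concern cost. The wording in 8.11 does concern cost.
- **Cost has no hypothesis, success criterion or sample size.** This stands and limits the weight of the point, although cost remains part of the primary objective.

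**Conclusion.** The point holds in conditional form. Stewardship team time is neither a listed cost item nor a collected quantity, while the assay is the only intervention component with its own cost. If the external model does not add the team's time, and if at least part of that time is incremental to usual care, the cost comparison favours PCT. The direction follows from arithmetic. The size cannot be derived from the documents: under assumed minutes, contacts and wages it runs from about 10 to a few hundred USD per PCT-arm patient before any reduction for time already spent under usual care. With no stated cost difference to set this against, its materiality is unknown.

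The analyses of shortABx, CAE30 and prescribedABx, the stopping rules and the sample size are not touched. The loss-of-function entry is a separate, minor inconsistency.

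**What to change.** 1. Add stewardship team time to the synopsis, 7.2 and 8.11 as a PCT-arm cost item: documented recommendations and discordance contacts per patient × stated minutes × staff rate, with a low and a high value. Alternatively, state in 8.11 that the model already includes it, and how.
2. Report the cost difference both with and without this item, and say how far the time is taken to be incremental to usual care.
3. State how assay cost is attributed to the arms, given that control-arm PCT is measured only for the study and suppressed.
4. In 8.11, describe the result as the cost of the PCT algorithm plus stewardship team against standard care.
5. Separately, reconcile loss of function with the hospital perspective and the data collected: give it a definition and a source, or take it out.

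The cost is a few sentences of protocol text and a stated assumption on unit time and staff rate. The contacts are already documented, so no new patient data are needed. The downside is a less favourable cost figure for PCT.
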